119 days. Bode and colleagues studied the safety and efficacy of Novolog insulin in 19
120 subjects used the same infusion set tubing for 7 days and overall, no negative effects
121 on glycemic control were observed during this period but it was noted that serum
122 glucose levels began to increase the longer the infusion set was used [17]. There have
123 been three published randomized trials assessing length of infusion set wear beyond 3
124 days. One study compared using insulin lispro to insulin aspart for 5 days of infusion set
125 wear [18]. There was no difference between the two insulins, with an average length of
126 infusion set wear of 98 and 96 hours, respectively. The researchers reported increased
127 glucose levels after 48 hours of wearing an infusion set and recommended changing
128 infusion sets every 2 days. We conducted a randomized, open-label, crossover study of
129 20 subjects who wore Teflon catheter (Quick-Set) and steel catheter (Sure-T) infusions
130 set for 38 weeks and 39 weeks respectively with no difference in the survival curves of
131 the infusion sets. The mean duration of wear was 5.5 days with a standard deviation of
132 1.9 days. Intersubject variation and the majority of failures were secondary to
133 uncorrectable hyperglycemia which indicates insulin flow occlusions [19]. Another
134 multicenter, crossover trial showed no difference in infusion set survival or mean
135 glucose in 20 type 1 diabetes subjects wearing the sets in either lipohypertrophied and
136 nonlipohypertrophied tissue [20].
137

138 **Etiology of Infusion Set Failures**

139 The underlying cause of intersubject variation in infusion set wear time is unknown but
140 in the prior infusion set studies time to failure was primarily associated with
141 hyperglycemia which did not improve with correction dose of insulin. In most of these
142 subjects, there was no overt back-pressure error from the pump. "Silent occlusions"
143 would be the most likely causative factor, and the additional slitted openings would
144 reduce the risk of silent occlusions and subsequent hyperglycemia (**Figure 2**). The
145 Lantern is designed to reduce failures due to kinking. Other less common causes for
146 set failure would probably not be affected by the Lantern; these include 10-15% being
147 pulled out by accident (tubing caught on a door handle for example), 6-12% from loss of
148 adhesiveness, 5-13% removed for pain and 5-10% for erythema/induration concerning

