218 cause of set failure. If a set is accidentally pulled out, it can be replaced by the subject.
219 Subjects will either complete a daily online questionnaire or they will be contacted daily
220 by research staff to determine if a set has failed, the cause of failure, and to record
221 measured erythema and edema at a failed infusion site. Failures are based on:
222

- 223 1. Presence of serum ketones with hyperglycemia
- 224 2. Unexplained hyperglycemia
3. Signs of infection at the infusion site

225 4. Pump occlusion alarm
226 5. Adhesive failure

227
228 Since infusion set failures will occur after variable lengths of wear, regularly scheduled
229 visits are unlikely to capture the day of an infusion set failure. Instead the subject will be
230 taught how to insert the set, measure erythema and induration with a ruler marked in
231 millimeters and to take a picture of the infusion site. Subjects will be instructed to text
232 the study team when they remove their infusion set and to send a picture of the infusion
233 site and measurements. If there is any evidence of an infection (≥ 10 mm of erythema or
234 induration), they will be asked to come in that day for an unscheduled visit.

[figure not shown]
235
236 Part 2: Extended Wear Randomized Controlled Crossover Study

237 This will be a masked, randomized controlled crossover study at Stanford University
238 (**Figure 4**). The study is intended for registration purposes and to support a 510(k)
239 submission. The planned duration of wear and visit schedule will be determined by the
240 results of Part 1. Participants, age 15 and over, will be randomized to wear the masked
241 investigational or control infusion set first. The control set is the Mio (used with
242 Medtronic pumps) or Inset II (used with other pump models) which are the precursors to
243 the Convatec Lantern and do not contain slits. Each participant will wear both the
244 investigational and control infusion set. Subjects will act as their own control.

245
246 At home subjects will examine their infusion site when they are changing an infusion set
247 and assess for signs of bleeding, local tissue reaction or infection. They will record
248 redness, induration, and bruising in mm, and call one of the investigators if there is
249 more than 10 mm of erythema or induration. They will be given a ruler for making these
250 measurements. If there is more than 3 mm of induration or redness they will be asked to

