474 labeling. While the G6 system is FDA approved for non-adjunctive use without
475 calibration, we will ask patients to confirm blood glucose with glucometer prior to
476 removing an infusion set. Subjects will be instructed to check blood ketones using a
477 blood ketone meter if there is unexplained hyperglycemia. Unexplained hyperglycemia
478 refers to high glucose levels outside of the usual times they may occur, such as in the
479 initial few hours following a meal. If the CGM stops functioning during the study, the
480 subjects will insert a new sensor which will be provided to them. If there is an
481 accidental removal of an infusion set the participant will have access to a replacement
482 which he or she will be taught to place.
483

484 *Determination of an infusion set failure:*

485 They will be instructed to replace the infusion set, in the following situations.

- 486 1. The presence of serum ketones >0.6 mmol/L with meter glucose >250 mg/dL, in
487 the absence of illness, vigorous fat burning exercise, starvation or alcohol.
- 488 2. Unexplained hyperglycemia, >250 mg/dL, outside anticipated periods of
489 carbohydrate consumption, illness, missed insulin doses and menstruation. This
490 hyperglycemia cannot be reduced with appropriate correction doses of insulin
491 (such as a decrease of at least 50 mg/dL in 1 hour following a correction dose).
- 492 3. Signs of infection at the infusion site including pain, erythema or induration >10
493 mm in diameter.
- 494 4. Pump occlusion alarm
- 495 5. Adhesive failure (only the adhesive on the infusion set will be used)

496
497 *Recording of infusion site information:* At home they will exam their infusion site each
498 day for signs of redness and/or induration. If they detect redness or induration they will
499 record them in mm and send a text to study staff. At the time an infusion set is removed
500 they will record redness and induration in millimeters, and call one of the investigators if
501 there is more than 10 millimeters of erythema or induration. They will be given a ruler
502 for making these measurements. Subjects will record the time and date that infusion
503 sets or sensors are removed, and document why they removed the set and take a
504 picture of the infusion site after the infusion set is removed if there is ≥ 3 mm of

505 induration or erythema. The picture and infusion site measurements will be sent via text

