506 or e-mail to study staff, if there is not concern about infection.

507

508 *Second infusion set placement:* After the duration of wear established from study part 1
509 elapses the patient will place the second infusion set type in the contralateral body area.
510 The same failure criteria and reporting will be used for the other set.

511

512 Final Visit

513 After the last infusion set was inserted, subjects will have their final study visit to
514 evaluate the infusion site. The insertion sites will be examined, erythema, induration and
515 local skin reaction will be measured and photographs taken for any significant changes.
516 Their insulin pump, CGM, blood glucose and ketone meter will be downloaded. All
517 infusion sets, glucose sensors, study pumps and transmitters provided by the study will
518 be returned. Additionally, the DSAT and DDS questionnaires will be repeated.

519 **CHAPTER 4: Adverse Event Reporting and Protocol Monitoring**

520 **Definition**

521 A reportable adverse event is any untoward medical occurrence that meets criteria for a
522 serious adverse event or any unexpected medical occurrence in a study subject that is
523 study or device-related. Skin irritation from sensor wear will be recorded in specific
524 sections of the case report forms. An adverse event form is only completed if skin
525 irritation is severe or antibiotics are required.

526

527 Hypoglycemic events are recorded as Adverse Events if the event required assistance
528 of another person due to altered consciousness to actively administer carbohydrate,
529 glucagon, or other resuscitative actions. This means that the subject was impaired
530 cognitively to the point that he/she was unable to treat him or herself, was unable to
531 verbalize his or her needs, was incoherent, disoriented, and/or combative, or
532 experienced seizure or coma. These episodes may be associated with sufficient
533 neuroglycopenia to induce seizure or coma. If plasma glucose measurements are not
534 available during such an event, neurological recovery attributable to the restoration of
535 plasma glucose to normal is considered sufficient evidence that the event was induced
536 by a low plasma glucose concentration.

537

538 Hyperglycemic events are recorded as Adverse Events if the event involved diabetic
539 ketoacidosis, as defined by the DCCT, and had all of the following:

- 540 1. Symptoms such as polyuria, polydipsia, nausea, or vomiting

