- 541 2. Serum ketones greater than 1.6 mM, or large/moderate urine ketones
- 542 3. Either arterial blood pH <7.30 or venous pH <7.24 or serum bicarbonate <15
- 543 4. Treatment provided in a health care facility

544

545 **Recording of Adverse Events**

546 Throughout the course of the study, all efforts will be made to remain alert to possible
547 adverse events or untoward findings. The first concern will be the safety of the subject,
548 and appropriate medical intervention will be made.

549

550 The investigator will elicit reports of adverse events from the subject at each visit and
551 complete all adverse event forms online. Each adverse event form is reviewed by the
552 Coordinating Center to verify the coding and the reporting that is required.

553

554 The study investigator will assess the relationship of any adverse event to be related or
555 unrelated by determining if there is a reasonable possibility that the adverse event may
556 have been caused by the study device or study procedures.

557

558 The intensity of adverse events will be rated on a three point scale: (1) mild, (2)
559 moderate, or (3) severe. It is emphasized that the term severe is a measure of
560 intensity: thus a severe adverse event is not necessarily serious. For example, itching
561 for several days may be rated as severe, but may not be clinically serious.

562

563

564 Adverse events that continue after the participant's discontinuation or completion of the
565 study will be followed until their medical outcome is determined or until no further
566 change in the condition is expected.

567

568 Adverse events will be coded using the MedDRA dictionary.

569

570 Definitions of relationship and intensity are listed on the website data entry form.

571

572 Adverse events that continue after the subject's discontinuation or completion of the
573 study will be followed until their medical outcome is determined or until no further
574 change in the condition is expected.

575

576 **Reporting Serious or Unexpected Adverse Events**

577 A serious adverse event is any untoward occurrence that: Results in death; is life-
578 threatening (a non life-threatening event which, had it been more severe, might have
579 become life-threatening, is not necessarily considered a serious adverse event);
580 requires inpatient hospitalization or prolongation of existing hospitalization; results in a

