581 disability or permanent damage which causes a substantial disruption of a person's
582 ability to conduct normal life functions; results in a congenital anomaly/birth defect;
583 requires intervention to prevent permanent impairment or damage (Devices); or any
584 other serious (Important Medical Event) which may jeopardize the patient and may
585 require medical or surgical intervention (treatment) to prevent a serious adverse event.

586

587 An Unanticipated Adverse Device Event is defined as an adverse event caused by, or
588 associated with, a device, if that effect or problem was not previously identified in
589 nature, severity, or degree of incidence.

590

591 Serious or unexpected adverse events must be reported to the Principal Investigator
592 immediately.

593 [name].
594 Division of Endocrinology and Diabetes
595 [name]
596 [name]
597 Office [contact]
598 Office [contact]

599

600 The principle investigator will notify all participating investigators of any adverse device
601 event that is both serious and unexpected. Notification will be made within 10 days after
602 becoming aware of the event.

603

604 Each investigator is responsible for informing his/her IRB of serious study-related
605 adverse events and abiding by any other reporting requirements specific to their IRB.

606

607 If a serious or unexpected adverse event occurs, the Principal Investigator will prepare
608 a report to the study sponsor within 5 days, and a report will also be sent to the IRB and
609 FDA within 10 days if the adverse event is serious or an unexpected device event. The

610 principal investigators will meet to decide the appropriate action to be taken, i.e.
611 continue study unmodified, modify study or stop study.

612

613 **Potential Risks and Side Effects**

614 Local Reaction

615 With insulin infusion sets there is a low risk for developing local skin infections which
616 may be increased by the prolonged wear of infusion sets from the recommended 3 days
617 to 10 days for this study. Itchiness, redness, bleeding, and bruising at the insertion site
618 might also occur. Local tape allergy is a possibility as well. These risks may also be
619 increased when patients use insulin infusion sets for longer than 3 days.

620

621 Invasive Testing

622 All subjects will be required to perform fingerstick blood glucose tests and fingerstick for

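### The adverse-event rule for skin reactions names the glucose sensor but not the infusion set under test, so the protocol does not clearly provide for grading, relationship, treatment and resolution of non-serious infusion-site infections.

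*Combined protocol and SAP*

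**What the plan says.** **Reporting rule.** Chapter 4, Definition, counts an event as reportable if it is serious, or if it is unexpected and related to the study or the device. Skin reactions come next: "study or device-related. Skin irritation from sensor wear will be recorded in specific" ... "sections of the case report forms. An adverse event form is only completed if skin" irritation is severe or needs antibiotics.

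**Expected risks.** Chapter 4, Local Reaction, begins "With insulin infusion sets there is a low risk for developing local skin infections which" and adds that prolonged wear may increase that risk. It also lists itching, redness, bleeding, bruising and tape allergy.

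**What follows from being an adverse event.** Chapter 4, Recording of Adverse Events, provides for a relationship assessment, a three-point intensity rating, MedDRA coding and continued follow-up ("Adverse events that continue after the participant's discontinuation or completion of the" study). Each is written for adverse events.

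**Set failure.** In Chapter 3, for both parts, failure criterion 3 is "Signs of infection at the infusion site including pain, erythema or induration >10" mm across. Subjects note why a set came out, measure redness and induration, and phone an investigator above 10 mm.

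**Suspected infection.** The Part 1 synopsis in Chapter 1 sets a threshold of 10 mm or more: "induration), they will be asked to come in that day for an unscheduled visit". The Part 2 synopsis asks for a call above 10 mm.

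**Purpose and prior rates.** Of Part 2 the synopsis says "The study is intended for registration purposes and to support a 510(k"). Chapter 1, Etiology of Infusion Set Failures, gives earlier causes of set failure, including "adhesiveness, 5-13% removed for pain and 5-10% for erythema/induration concerning" for infection. Chapter 6 lists cause of failure, erythema and induration as exploratory outcomes.

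**The concern.** The infusion set is the product being tested, and local infection is a harm that the protocol itself says extended wear may increase. Yet the only skin-reaction rule is introduced for the sensor, which is not under test, and the general definition leaves out expected, non-serious, device-related events. Together these two features leave it unclear whether a set taken out for signs of infection ever enters the adverse-event system.

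The stake is the quality of the safety comparison in Part 2. Someone assessing the device would want to know how bad each suspected infection was, whether it was attributed to the set, how it was treated and whether it cleared, by set type. The written plan does not secure that.

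**Working it through.** The plan states no figure on this point, so the check is a reading of the rules together, followed by a calculation of scale.

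**Step 1. Is a non-serious infusion-site infection reportable under the general definition?** It must be unexpected as well as related. Local Reaction lists it as a known risk, so it is expected. It falls outside.

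**Step 2. Does the skin-reaction rule bring it back in?** There are two readings.
- *Narrow.* The threshold sentence (severe, or antibiotics needed) continues the sensor sentence and covers the sensor only. The infusion site then has no rule.
- *Broad.* The threshold sentence names no device, and Chapter 4, Other Risks, speaks of skin irritation from the adhesive of either the sensor or the infusion set. Infusion-site reactions that are severe or need antibiotics then get a form. Milder criterion 3 removals still do not.

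**Step 3. What is lost without a form?** Relationship, intensity, coding and follow-up to outcome, because the recording rules attach these to adverse events. No sentence says that a criterion 3 removal is an adverse event.

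**Step 4. What is captured by another route?** For both set types: reason for removal, mm of redness and induration, and a call above 10 mm. The Part 2 final visit examines, measures and, where changes are significant, photographs the sites, but its timing is given only as after the last set is inserted. The Part 1 final visit mentions only return of equipment. None of these passages asks for treatment, relationship or resolution.

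**Step 5. Scale.** Inputs: 24 Part 1 subjects with one Lantern set each; 40 Part 2 subjects × 2 sets = 80 sets (Chapter 2); 5-10% for erythema or induration suggesting infection (Chapter 1). Replacement sets are ignored.

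The 5-10% is a share among causes of failure, so the expected count = sets × proportion failing × share.

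| Assumption | At 5% | At 10% |
|---|---|---|
| Part 1, all 24 fail | 24 × 0.05 = 1.2 | 24 × 0.10 = 2.4 |
| Part 2, all 80 fail | 80 × 0.05 = 4 | 80 × 0.10 = 8 |
| Both parts, all 104 fail | 5.2 | 10.4 |
| Part 2 Lantern, 20% of 40 fail (8 sets) | 8 × 0.05 = 0.4 | 8 × 0.10 = 0.8 |
| Part 2 control, all 40 fail | 40 × 0.05 = 2 | 40 × 0.10 = 4 |
| Part 2 total, last two rows | 2.4 | 4.8 |

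The 20% is an assumption: Part 1 looks for the wear time at which 80% of Lantern sets still work, and I suppose that Part 2 uses that time and that Lantern performs the same there. Criterion 3 also names pain, which the protocol gives separately as 5-13%. It is not clear whether pain alone triggers the criterion, and I have not counted it.

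**Step 6. Suspected infection, side by side.** The Part 1 synopsis has a same-day visit at 10 mm or more. Chapter 3 for Part 1, Chapter 3 for Part 2 and the Part 2 synopsis all have a call above 10 mm. The mismatch is therefore within Part 1 as well as between the parts.

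**The case against.** The strongest reply is that this is a matter of classification, not of lost data. Staff learn of every removal, the cause and the measurements are outcome data, and the same criteria and reporting apply to both sets. This stands. A reader might infer that infections go unrecorded, or that the two sets cannot be compared on them. The documents do not support that: removals for infection signs can be counted by set type.

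A second reply is that the threshold sentence names no device, so the cases that matter most would get a form. This is a fair reading, and it rules out saying that the adverse-event tables would hold few or no site infections, which is true only on the narrow reading. It does not settle which reading applies, and it leaves milder removals outside.

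Third, Chapter 4 does not treat expected reactions as ungradable throughout. Its example of a severe but non-serious event is prolonged itching, itself a listed reaction. An event not previously identified in severity or degree of incidence can also qualify as an unanticipated device event, and serious events are always reportable. These points stand. They show that the text pulls in two directions, not that an ordinary site infection is covered.

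Fourth, criterion 3 concerns signs, so a removal under it is not a diagnosed infection. The case report forms are also not in the documents and may hold fields for treatment and resolution. Both points are right. The finding is that the protocol does not provide for these items, not that they will be absent.

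Finally, one might infer that Part 2 subjects get weaker clinical follow-up than Part 1 subjects. The Chapter 3 procedures are the same for both parts, and a call to an investigator does not exclude a visit. What remains is a synopsis that disagrees with the procedures.

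**Conclusion.** The point holds as a gap in the adverse-event rule. Read literally, a non-serious infection at the study infusion set needs no form, rating or follow-up to outcome. Read broadly, that is still so for removals for infection signs that are neither severe nor treated with antibiotics. The protocol should not leave the choice of reading open in a study meant to support a 510(k).

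The numbers are small. With every set failing, about 4-8 of 80 Part 2 sets and 1-2 of 24 Part 1 sets are involved. These are ceilings, not forecasts, because the 5-10% is a share of failures and not of sets worn. With 20% of Lantern sets and all control sets failing, Part 2 gives about 2.4-4.8. Both ranges assume that the earlier share carries over; the protocol's own statement that longer wear may increase local infection means that it could be higher.

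This does not threaten the primary comparison. It is a cheap improvement to the safety record.

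**What to change.** 1. In Chapter 4, Definition, extend the skin-reaction rule from sensor wear to *sensor or infusion-set wear*, so that severe or antibiotic-treated infusion-site reactions clearly need an adverse event form.
2. For every study set removed under failure criterion 3, expected or not, record set type, relationship, intensity, treatment given and date resolved. Use either an adverse event form, written as an explicit exception to the severe-or-antibiotics threshold, or the dedicated case report form section. Without the explicit exception, that threshold would still exclude the milder cases from the form.
3. Follow these events to resolution, as the existing rule does for adverse events, and tabulate them by set type.
4. Reconcile the Part 1 synopsis (same-day visit, 10 mm or more) with the Chapter 3 procedures for both parts (call, above 10 mm). Which procedure and threshold apply is for the investigators to decide.

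The cost is protocol wording and a few extra forms, at most about 5-10 over both parts on the figures above. The downside is an adverse-event table that looks somewhat less favourable.

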743 Before beginning a larger cross-over study we would perform this pilot study to
744 determine the maximum length of Lantern infusion set wear when 80% are still
745 functional if failure was not due the infusion set being accidentally pulled out. This study
746 is not statistically powered.

747

748 **Part 2**

749 Primary Outcome

750 Our primary outcome will be time to failure of each infusion set. We have reviewed 353
751 weeks of infusion set wear from prior studies [19-20, unpublished data] and subjects
752 who wear the control set have an average length of wear of 5.1 days with a standard
753 deviation of 1.7 days and intra-subject correlation of 0.69. For a meaningful clinical
754 benefit, the subjects who wear the treatment set should extend wear by at least 1 day to
755 an average length of wear of 6.1 days. A sample size of 40 subjects will provide 95%
756 power to detect a difference of 1 day in the average length of wear in a two-sided test
757 with an alpha level of 0.05. A minimum of 25 subjects must be recruited for 80% power.

758

759 Exploratory Outcomes

760 Other outcomes will include – BMI, cause of infusion set failure, measurements of
761 erythema and induration, pump insulin delivery data, glucometer readings, ketone meter
762 data, average daily CGM blood glucose, DSAT/DDS score and infusion set
763 questionnaire.

764

765 We will summarize the other secondary measures using means, standard deviation,
766 medians, ranges, proportions and 95% confidence interval, as appropriate. We will also
767 explore the relationship between BMI, DSAT/DDS score and the time to failure primary
768 outcome. Finally, we will test if there is a significant change in the DSAT/DDS score
769 following participation in the clinical trial.

770 **CHAPTER 7: References**

1. The Diabetes Control and Complications Trial Research Group. "The effect of intensive treatment of diabetes on the development and progression of long-term complications in insulin-dependent diabetes mellitus. The Diabetes Control and Complications Trial Research Group." *N Engl J Med.* 1993 Sep 30;329(14):977-86.
2. Diabetes Control and Complications Trial/Epidemiology of Diabetes Interventions and Complications (DCCT/EDIC) Study Research Group. "Intensive diabetes treatment and cardiovascular disease in patients with type 1 diabetes." *N Engl J Med.* 2005 Dec 22;353(25):2643-53.

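### The stated 95% power with 40 subjects and minimum of 25 for 80% power do not follow from the stated SD of 1.7 days and correlation of 0.69

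*Combined protocol and SAP*

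**What the plan says.** Chapter 1, Protocol Synopsis, Part 2 describes a crossover in which every participant wears both the "investigational and control infusion set. Subjects will act as their own control". Chapter 2, Study Enrollment and Duration, gives 40 subjects for Part 2.

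The sample-size reasoning is one paragraph in Chapter 6, Part 2, Primary Outcome:

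- Endpoint: "Our primary outcome will be time to failure of each infusion set", powered as a difference in mean length of wear.
- Variability, from prior studies and unpublished data: subjects "who wear the control set have an average length of wear of 5.1 days with a standard" "deviation of 1.7 days and intra-subject correlation of 0.69".
- Target difference: 1 day, from 5.1 to 6.1 days, tested two-sided at alpha 0.05.
- Results: "A sample size of 40 subjects will provide 95" percent power, and "A minimum of 25 subjects must be recruited for 80% power".

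The paragraph names no test or formula. It gives no SD for the Lantern set, no SD of the within-subject difference and no dropout allowance.

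**The concern.** In a paired design, an intra-subject correlation is quoted so that the between-subject SD can be converted into the SD of the difference. A correlation as high as 0.69 makes the SD of the difference clearly smaller than 1.7 days. The stated sample sizes look too large for that, as if the conversion had not been made.

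At stake is whether the only sample-size justification for Part 2 can be relied on. The synopsis says Part 2 is meant for registration and to support a 510(k) submission, so an outside reader is likely to try to reproduce it. As written, that reader cannot tell whether the trial has 95% or more than 99% power for a 1-day gain, or whether 25 is really the number needed for 80%. Any later recalculation, for dropout or for the wear limit that Part 1 will set, also needs the correct SD of the difference as its starting point.

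**Working it through.** **Inputs** (all from Chapter 6, Part 2, Primary Outcome, except the paired design, which is in the synopsis): SD 1.7 days, correlation ρ = 0.69, difference 1 day, two-sided alpha 0.05, N = 40 and N = 25. Two assumptions are mine, because the plan is silent: a paired t-test, and the same SD on both sets.

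**Formulas.** SD of the within-subject difference: SD_d = 1.7 × √(2 × (1 − ρ)). Power comes from the noncentral t distribution with n − 1 degrees of freedom and noncentrality √n × 1 / SD_d.

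**Step 1: reproduce the plan's figures.** Put SD_d = 1.70 days, that is, use 1.7 directly as the SD of the difference. With equal SDs this corresponds to ρ = 0.50, since √(2 × 0.50) = 1.

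- N = 24 gives 78.8% and N = 25 gives 80.6%, so the minimum for 80% is 25.
- N = 39 gives 94.7% and N = 40 gives 95.2%, so the minimum for 95% is 40.

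Both stated sample sizes come out exactly. Solving in reverse, 95% at 40 implies SD_d = 1.711 and 80% at 25 implies SD_d = 1.712.

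**Step 2: use the inputs as written.** SD_d = 1.7 × √(2 × 0.31) = 1.7 × 0.7874 = 1.339 days.

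| | Stated | SD 1.7, ρ = 0.69 (SD_d 1.339) | SD_d = 1.70 |
|---|---|---|---|
| Power at N = 40 | 95% | 99.6% | 95.2% |
| Power at N = 25 | 80% | 94.8% | 80.6% |
| Minimum N for 80% | 25 | 17 | 25 |
| Minimum N for 95% | 40 | 26 | 40 |

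In the middle column, N = 16 gives 79.7% and N = 17 gives 82.4%. The difference detectable with 95% power at N = 40 is 1.339 / 1.711 = 0.78 day.

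**Step 3: try other routes to the stated figures.**

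- Analysis details, keeping SD 1.7 and ρ = 0.69: n − 2 degrees of freedom gives 99.6% and 17; a normal approximation gives 99.7% and 15. Rounding of ρ (0.685 to 0.695) gives 99.5% to 99.6%, and 17 or 16.
- Larger SD: 1.9 days (from the earlier crossover cited in Background and Rationale) with ρ = 0.69 gives 98.5% and 20. A Lantern SD scaled to its mean, 1.7 × 6.1 / 5.1 = 2.03 days, gives 98.4% and 20.
- Different alpha: one-sided 0.05 gives 99.9% and 13. Two-sided 0.01 gives 97.4% and 25, matching one figure but contradicting the stated alpha.
- No correlation (ρ = 0): 72.8% and 48. Two independent groups of 40: 74.9%.
- A factor (1 − ρ²) in place of (1 − ρ): 94.3% at 40, 26 for 80% and 42 for 95%. This is close, but it misses both stated sample sizes and is not the variance of a paired difference.
- Hidden dropout allowance: going from 17 to 25 needs a loss of 1 − 17/25 = 32%, and from 26 to 40 a loss of 1 − 26/40 = 35%. No such allowance is stated.

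**The case against.** The strongest objection is that the plan gives an SD only for the control set. If the Lantern SD were 2 × 0.69 × 1.7 = 2.35 days, the variance of the difference would be 1.7² + 2.35² − 2 × 0.69 × 1.7 × 2.35 = 2.89. SD_d would then be 1.70 days, and 40 and 25 would follow with 0.69 in use. This is algebraically right, so the statement that the correlation was left out is an inference and not a proof. But it needs a Lantern SD 38% larger than the control SD, a figure found nowhere in the protocol, and one that happens to return exactly 1.70. The mismatch between the written inputs and the written results remains.

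A second objection is that the stated power may be correct. If 1.7 days was the SD of paired differences in the prior data, only its label is wrong. That is possible, and the protocol cannot settle it because part of the source is unpublished. The finding is therefore that inputs and outputs disagree, not that 99.6% and 17 are the true values.

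A third is that little follows in practice. This stands in large part. If the written inputs are right, 40 subjects are more than enough: assuming 10% or 20% dropout, 36 or 32 evaluable subjects would still give 99.2% or 98.3% power. If 1.7 is the SD of differences, the stated figures hold. The minimum of 25 is also a power figure, not tied to any stopping or continuation rule.

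**Conclusion.** The concern holds. Taken as written, SD 1.7 days and correlation 0.69 give 99.6% power at 40 subjects where 95% is stated, and a minimum of 17 for 80% power where 25 is stated: 4.6 percentage points and 8 subjects apart. The likeliest explanation is that 1.7 was entered as the SD of the within-subject difference, which reproduces both stated sample sizes exactly.

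The result rests on a paired t-test, equal SDs on the two sets and uncensored, roughly normal wear times. The choice of test matters little; the equal-SD assumption matters more, as shown above. Dropout and the cap on wear time to be set by Part 1 are not part of the plan's calculation and were not modelled here. This should be corrected, but it does not threaten the adequacy of 40 subjects under either plausible reading.

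**What to change.** Rewrite the sample-size paragraph in Chapter 6, Part 2 so that it names the test, gives the SD of the within-subject difference that was used, and says where that SD comes from. Then go back to the prior data and take whichever course they support:

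- If 1.7 days is the SD of wear time on a set and 0.69 is the correlation, state SD_d = 1.34 days and the equal-SD assumption. Restate power as 99.6% at 40 and the minimum for 80% as 17, or report 0.78 day as the difference detectable with 95% power at 40.
- If 1.7 days is the SD of paired differences, say so, keep 95% and 25, and remove 0.69 as an input to the calculation.
- If a larger SD was assumed for the Lantern set, state it.

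The text should not describe the choice as deliberately conservative unless the sponsor's records show that it was. Any further power calculation that allows for dropout or for the wear limit should use the same SD of the difference. The cost is one paragraph; the planned 40 subjects need not change.
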